**Table 4 Infusion Reaction Treatment Guidelines**

NCI CTCAE Grade	Treatment	Premedication at subsequent dosing
Grade 1 Mild reaction; infusion interruption not indicated; intervention not indicated	Increase monitoring of vital signs as medically indicated until the subject is deemed medically stable in the opinion of the investigator.	None
Grade 2 Requires infusion interruption but responds promptly to symptomatic treatment (e.g., antihistamines, NSAIDS, narcotics, IV fluids); prophylactic medications indicated for < =24 hrs	
Stop Infusion and monitor symptoms.                      Additional appropriate medical therapy may include but is not limited to:
 
IV fluids                      Antihistamines                      NSAIDS                      Acetaminophen                      Narcotics
 
Increase monitoring of vital signs as medically indicated until the subject is deemed medically stable in the opinion of the investigator.                      If symptoms resolve within one hour of stopping drug infusion, the infusion may be restarted at 50% of the original infusion rate (e.g., from 100 mL/hr to 50 mL/hr). Otherwise dosing will be held until symptoms resolve and the subject should be premedicated for the next scheduled dose.
 
Subjects who develop Grade 2 toxicity despite adequate premedication should be permanently discontinued from further trial treatment administration.
	Subject may be premedicated 1.5h ( $\pm$ 30 minutes) prior to infusion of pembrolizumab (MK-3475) with:  Diphenhydramine 50 mg po (or equivalent dose of antihistamine).  Acetaminophen 500-1000 mg po (or equivalent dose of antipyretic).
Grades 3 or 4  Grade 3: Prolonged (i.e., not rapidly responsive to symptomatic medication and/or brief interruption of infusion); recurrence of symptoms following initial improvement; hospitalization indicated for other clinical sequelae (e.g.,	
Stop Infusion.                      Additional appropriate medical therapy may include but is not limited to:
 
IV fluids                      Antihistamines                      NSAIDS                      Acetaminophen                      Narcotics                      Oxygen                      Pressors                      Corticosteroids                      Epinephrine
	No subsequent dosing

NCI CTCAE Grade	Treatment	Premedication at subsequent dosing
renal impairment, pulmonary infiltrates)  Grade 4: Life-threatening; pressor or ventilatory support indicated	Increase monitoring of vital signs as medically indicated until the subject is deemed medically stable in the opinion of the investigator. Hospitalization may be indicated. Subject is permanently discontinued from further trial treatment administration.	
Appropriate resuscitation equipment should be available in the room and a physician readily available during the period of drug administration.		

## 5.5 Diet/Activity/Other Considerations

### 5.5.1 Diet

Subjects should maintain a normal diet unless modifications are required to manage an AE such as diarrhea, nausea or vomiting.

### 5.5.2 Contraception

Pembrolizumab may have adverse effects on a fetus in utero. Furthermore, it is not known if pembrolizumab has transient adverse effects on the composition of sperm.

For this trial, male subjects will be considered to be of non-reproductive potential if they have azoospermia (whether due to having had a vasectomy or due to an underlying medical condition).

Female subjects will be considered of non-reproductive potential if they are either:

(1) postmenopausal (defined as at least 12 months with no menses without an alternative medical cause; in women < 45 years of age a high follicle stimulating hormone (FSH) level in the postmenopausal range may be used to confirm a post-menopausal state in women not using hormonal contraception or hormonal replacement therapy. In the absence of 12 months of amenorrhea, a single FSH measurement is insufficient.);

OR

(2) have had a hysterectomy and/or bilateral oophorectomy, bilateral salpingectomy or bilateral tubal ligation/occlusion, at least 6 weeks prior to screening;

OR

(3) has a congenital or acquired condition that prevents childbearing.

Female and male subjects of reproductive potential must agree to avoid becoming pregnant or impregnating a partner, respectively, while receiving study drug and for 120 days after the last dose of study drug by complying with one of the following:

(1) practice abstinence† from heterosexual activity;

OR

(2) use (or have their partner use) acceptable contraception during heterosexual activity.

Acceptable methods of contraception are‡:

Single method (one of the following is acceptable):

- intrauterine device (IUD)
- vasectomy of a female subject's male partner
- contraceptive rod implanted into the skin

Combination method (requires use of two of the following):

- diaphragm with spermicide (cannot be used in conjunction with cervical cap/spermicide)
- cervical cap with spermicide (nulliparous women only)
- contraceptive sponge (nulliparous women only)
- male condom or female condom (cannot be used together)
- hormonal contraceptive: oral contraceptive pill (estrogen/progestin pill or progestin-only pill), contraceptive skin patch, vaginal contraceptive ring, or subcutaneous contraceptive injection

†Abstinence (relative to heterosexual activity) can be used as the sole method of contraception if it is consistently employed as the subject's preferred and usual lifestyle and if considered acceptable by local regulatory agencies and ERCs/IRBs. Periodic abstinence (e.g., calendar, ovulation, sympto-thermal, post-ovulation methods, etc.) and withdrawal are not acceptable methods of contraception.

‡If a contraceptive method listed above is restricted by local regulations/guidelines, then it does not qualify as an acceptable method of contraception for subjects participating at sites in this country/region.

Subjects should be informed that taking the study medication may involve unknown risks to the fetus (unborn baby) if pregnancy were to occur during the study. In order to participate in the study subjects of childbearing potential must adhere to the contraception requirement (described above) from the day of study medication initiation (or 14 days prior to the initiation of study medication for oral contraception) throughout the study period up to 120 days after the last dose of trial therapy. If there is any question that a subject of childbearing potential will not reliably comply with the requirements for contraception, that subject should not be entered into the study.

### **5.5.3 Use in Pregnancy**

If a subject inadvertently becomes pregnant while on treatment with pembrolizumab, the subject will immediately be removed from the study. The site will contact the subject at least monthly and document the subject's status until the pregnancy has been completed or terminated. The outcome of the pregnancy will be reported to the Sponsor and to Merck without delay and within 24 hours to the Sponsor and within 2 working days to Merck if the outcome is a serious adverse experience (e.g., death, abortion, congenital anomaly, or other disabling or life-threatening complication to the mother or newborn).

The study investigator will make every effort to obtain permission to follow the outcome of the pregnancy and report the condition of the fetus or newborn to the Sponsor. If a male subject impregnates his female partner the study personnel at the site must be informed immediately and the pregnancy reported to the Sponsor and to Merck and followed as described above and in Section 7.2.2.

#### **5.5.4 Use in Nursing Women**

It is unknown whether pembrolizumab is excreted in human milk. Since many drugs are excreted in human milk, and because of the potential for serious adverse reactions in the nursing infant, subjects who are breast-feeding are not eligible for enrollment.

#### **5.6 Subject Withdrawal/Discontinuation Criteria**

Subjects may withdraw consent at any time for any reason or be dropped from the trial at the discretion of the investigator should any untoward effect occur. In addition, a subject may be withdrawn by the investigator or the Sponsor if enrollment into the trial is inappropriate, the trial plan is violated, or for administrative and/or other safety reasons. Specific details regarding discontinuation or withdrawal are provided in Section 7.1.4 – Other Procedures.

A subject must be discontinued from the trial for any of the following reasons:

- The subject or legal representative (such as a parent or legal guardian) withdraws consent.
- Unacceptable adverse experiences as described in Section 5.2.1.2
- Intercurrent illness that prevents further administration of treatment
- Investigator's decision to withdraw the subject
- The subject has a confirmed positive serum pregnancy test
- Noncompliance with trial treatment or procedure requirements
- The subject is lost to follow-up
- Administrative reasons

The End of Treatment and Follow-up visit procedures are listed in Section 6 (Protocol Flow Chart) and Section 7.1.5 (Visit Requirements). After the end of treatment, each subject will be followed for 30 days for adverse event monitoring (serious adverse events will be collected for 90 days after the end of treatment as described in Section 7.2.3.1). Subjects who discontinue for reasons other than progressive disease will have post-treatment follow-up for disease status until disease progression, initiating a non-study cancer treatment, withdrawing consent or becoming lost to follow-up. After documented disease progression each subject will be followed by telephone for overall survival until death, withdrawal of consent, or the end of the study, whichever occurs first.

#### **5.7 Subject Replacement Strategy**

Subjects receiving less than 2 doses of pembrolizumab may be replaced but will be monitored for study specified outcomes. Subjects removed from the trial for toxicities / SAEs probably or definitely related to pembrolizumab will not be replaced.

#### **5.8 Clinical Criteria for Early Trial Termination**

As a feasibility trial in which patients may receive the standard of care in addition to pembrolizumab therapy at the discretion of the treating physician, stopping rules for FUTILITY are not indicated.

Stopping rules for TOXICITY are outlined in section 8

Early trial termination will be the result of the criteria specified below:

1. Quality or quantity of data recording is inaccurate or incomplete

2. Poor adherence to protocol and regulatory requirements
3. Incidence or severity of adverse drug reaction in this or other studies indicates a potential health hazard to subjects
4. Plans to modify or discontinue the development of the study drug

In the event of Merck decision to no longer supply study drug, ample notification will be provided so that appropriate adjustments to subject treatment can be made.

## 6.0 TRIAL FLOW CHART

Study Period:	Screening Phase		Treatment Cycles Phase I: Induction				Response Post- Induction	Treatment Cycles Phase II: Maintenance	Response Post- Maintenance	Post-Treatment	
Treatment Dose/Title Day (D)	Pre- screening	Main Study Screening	1 (D1)	2 (D22)	3 (D43)	4 (D64)	(D77)	Doses 5 – 17 (D85 - D365)*	End of Treatment (D365)	Follow-up: 30 and 90 Days After Treatment up to D455†	Relapse‡
Scheduling Window (Days):	Days -21 to -1	Days -21 to -1	± 3	± 3	± 3	± 3	±7	± 3	± 14	± 14	n/a
Administrative Procedures											
Informed Consent		X									
Inclusion/Exclusion Criteria	X	X									
Subject Identification Card		X									
Demographics and Medical History		X									
Prior and Concomitant Medication Review		X					X				
Study Treatment Administration			X	X	X	X		X			
Post-study Therapy Response Status									X		
Survival Status									X		X
Clinical Procedures/Assessments											
Review Adverse Events		X	X	X	X	X	X	X	X	X	
Full Physical Examination		X	X	X	X	X	X				
Directed Physical Examination								X	X	X	
Vital Signs and Weight		X	X	X	X	X	X	X	X	X	
ECOG OR Karnofsky Performance Status		X	X	X	X	X	X	X			
Laboratory Procedures/Assessments: analysis performed by LOCAL laboratory											
Pregnancy Test – Urine or Serum b-HCG		X	X	X	X	X	X				
PT/INR and aPTT		X	X	X	X	X					
CBC with Differential		X	X	X	X	X	X	X	X	X	
Comprehensive Serum Chemistry Panel		X	X	X	X	X	X	X	X	X	
LDH and Uric acid		X	X	X	X	X					
Urinalysis		X	X	X	X	X		X			

Study Period:	Screening Phase		Treatment Cycles Phase I: Induction				Response Post- Induction	Treatment Cycles Phase II: Maintenance		Response Post- Maintenance	Post-Treatment	
Treatment Dose/Title Day (D)	Pre- screening	Main Study Screening	1 (D1)	2 (D22)	3 (D43)	4 (D64)	(D77)	Doses 5 – 17 (D85 - D365)*		End of Treatment (D365)	Follow-up: 30 and 90 Days After Treatment up to D455†	Relapse‡
Scheduling Window (Days):	Days -21 to -1	Days -21 to -1	± 3	± 3	± 3	± 3	±7	± 3		± 14	± 14	n/a
T3, FT4 and TSH		X	X	X	X	X		X				
Efficacy Measurements												
Bone Marrow Morphology§				D35 (±5)			X			X		X
Bone Marrow Flow Cytometry§				D35 (±5)			X			X		X
Bone Marrow Cytogenetics§				D35 (±5)			X			X		X
Tumor Biopsies/Archival Tissue Collection/Correlative Studies Blood												
Pre-transplant Bone Marrow Biopsy Specimen Collection		X										
Correlative Studies: Bone Marrow Aspirate§		X		D35 (±5)			X			X		X
Correlative Studies: Blood Collection§, ¶		X	D14 (+5)	D35 (±5)	D56 (±5)		X	D168 (±7) D252 (±7)		X	D425 (±14)†	X
Correlative Studies: Buccal Swabs		X										
Chimerism Analysis (VNTR) (Peripheral Blood)**		X		X			X			X		X

\*Phase II Maintenance treatment: For subjects achieving CR / PR as determined by day 77 response post-induction without significant pembrolizumab related toxicity. Subjects without CR / PR at day 77, relapse / progression after day 77 or clinically significant toxicity during the treatment will be considered off treatment and will be placed into follow-up.

†Follow up: Toxicity assessments will be for 30 days after last dose of pembrolizumab. Longer follow-up for up to 90 days, if applicable, based on continuing SAE / AE that was observed in the treatment period or an events of clinical interest (ECI). Follow up for survival will be up to 90 days after pembrolizumab or D455 (±14) for subjects completing

maintenance and a research blood collection will be obtained. Subjects not initiating or completing maintenance will complete 30 day toxicity assessments and then be followed only for survival (through D365 after initiating pembrolizumab). Subjects in CR/PR not completing maintenance for toxicity may have additional research specimens collected per investigators discretion (see below note). ‡ Relapse denotes collection of unplanned / unscheduled bone marrow aspirate, biopsy and correlative studies at time of clinical suspicion of relapse (if CR) or progression of malignancy at any time during treatment and follow-up periods.

§Bone marrow morphology based on aspirate and/or core biopsy, flow cytometry and  $\pm$  cytogenetics will be performed on day 35 (+5) after dose #2, day 77 ( $\pm$ 7) after dose #4, day 365 ( $\pm$ 14) after completing maintenance. An end of treatment bone marrow may be performed prior to day 365 in subjects in CR/PR who do not complete full maintenance therapy due to toxicity. Subjects removed from further treatment due to documented relapse are not required to undergo further bone marrow studies for research purposes. Cytogenetic analysis may be omitted if there are not pre-treatment cytogenetic anomalies of clinical interest.

||Comprehensive Serum Chemistry Panel should include Magnesium and Phosphorus.

¶ PK and anti-pembrolizumab Ab testing may be performed as a component of the research lab testing, as indicated. These studies will be performed after collaboration with the sponsor (Merck)

\*\* Chimerism studies (lineage specific) when sent as part of routine care will be recorded as percentage of donor cells (CD3 and CD33).

Note: Every effort will be made to collect bone marrow and blood samples for efficacy and correlative specimens for research purposes. Efficacy and correlative studies not obtained during the treatment and post-treatment for clinical reasons (e.g. intercurrent illness, leukemia progression receiving concomitant chemotherapy, myeloid sarcoma) will not constitute a protocol deviation.

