**Secondary objective endpoints:**

- Estimate overall survival (OS) and disease-free survival (DFS) at one year in patients who receive pembrolizumab for relapse after allogeneic HCT.

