#### **7.1.4.5 Follow-up Visits**

Every effort should be made to collect information regarding disease status until the start of new anti-neoplastic therapy, disease progression, death, end of the study or if the subject begins retreatment with pembrolizumab as detailed in Section 7.1.4.5.1.

Subjects in this trial will not be eligible for retreatment with pembrolizumab beyond the initial study phase.

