##### **7.1.4.5.1 Survival Follow-up**

If a subject experiences a treatment related adverse event that necessitates their removal from further study treatment, starts a new anti-cancer therapy (non-protocol defined therapy), does not achieve after induction (phase I), develops progression during maintenance (phase II) or completes planned treatment phase the subject moves from treatment into the survival follow-up phase and will be followed at a minimum of every 8 weeks to assess for survival status until death, withdrawal of consent, or the end of the study (1 year after initiation of pembrolizumab or 90 days after last maintenance dose of pembrolizumab), whichever occurs first (please reference section 5.2.1.2 of this protocol regarding permitted chemotherapies on-protocol). These visits will be coordinated with routine BMT follow-up. If follow-up is not feasible (e.g. patient leaves center) phone contacts will be made every 12 weeks.

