## **8.0 STATISTICAL ANALYSIS PLAN**

### **8.1 Statistical Analysis Plan Summary**

The statistical plan for this feasibility study of pembrolizumab for relapse after HCT is primarily directed toward the primary objective of safety and feasibility after HCT. The trial will additionally estimate the proportion of patients responding to pembrolizumab monotherapy by overall response rate (ORR). The ORR (CR+PR) will also be estimated at day 35 and 77 for subjects receiving  $\geq$  one dose of single agent pembrolizumab. If progression is noted subjects may receive standard induction chemotherapy. Subjects who are administered standard induction chemotherapy prior to day 77 (for any reason) will be considered non-responders for ORR of pembrolizumab monotherapy. However, we will perform a planned subset analysis to determine the ORR at day 77 for subjects receiving pembrolizumab followed by systemic chemotherapy.

The incidence of grade 3-4 acute GvHD and significant ( $\geq$  grade 3) immune mediated toxicities will be estimated at the conclusion of the treatment period which is 30 days after the last dose of pembrolizumab. Overall survival (OS) and Disease Free Survival (DFS) at 12 months will be calculated by Kaplan Meier methods. The observation period for OS and DFS will begin at the confirmed date of relapse after HCT until death or last scheduled clinical follow up. These observations will assist in determining whether further investigations are warranted after HCT.

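### Flow chart and 7.1.4.5.1 schedule survival status only after an early stop without progression, while 5.6 requires disease-status follow-up, so a later relapse can go undated and one-year DFS can be biased

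*Combined protocol and SAP*

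**What the plan says.** Four places govern follow-up of a subject who leaves treatment without progression.

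- **6.0 Trial Flow Chart, footnote †:** "Subjects not initiating or completing maintenance will complete 30 day toxicity assessments and then be followed only for survival". The footnote runs this through D365.
- **7.1.4.5.1 Survival Follow-up:** a subject removed for a treatment-related adverse event moves into this phase and "will be followed at a minimum of every 8 weeks to assess for survival status until death". Where visits are not feasible, phone contact every 12 weeks replaces them.
- **5.6 Subject Withdrawal/Discontinuation Criteria:** "Subjects who discontinue for reasons other than progressive disease will have post-treatment follow-up for disease status until disease progression". Telephone follow-up for survival starts only after documented progression.
- **7.1.4.5 Follow-up Visits:** "Every effort should be made to collect information regarding disease status until the start of new anti-neoplastic therapy, disease progression, death", with end of study also listed as an end point.

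The endpoint concerned is secondary: "Estimate overall survival (OS) and disease-free survival (DFS) at one year in patients who receive pembrolizumab for relapse after allogeneic HCT". On analysis, 8.1 says "Overall survival (OS) and Disease Free Survival (DFS) at 12 months will be calculated by Kaplan Meier methods" and then "The observation period for OS and DFS will begin at the confirmed date of relapse after HCT until death or last scheduled clinical follow up". It does not say what counts as a DFS event or on what date a subject without an event is censored. Section 7.1.3.1.3 also plans Cox regression for PFS and competing-risks regression for relapse or progression in the correlative work.

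**The concern.** The conflict is about what is asked at follow-up contacts. When follow-up ends is a separate matter.

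The subject who falls into the gap is foreseeable. Section 5.2.1.2 ends pembrolizumab permanently for acute GvHD of grade 3 or higher that needs systemic corticosteroids, and the flow-chart footnotes themselves mention subjects in CR or PR who do not complete maintenance because of toxicity. Under the flow chart such a person is contacted for survival status. Under 5.6 the same person is followed for disease status.

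If a site works from the flow chart, a relapse after the stop may have no recorded date. One-year DFS and the relapse/progression regression both need that date, and it may be hard to recover afterwards.

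**Working it through.** **No plan figure to reproduce.** The documents state no DFS rate, and no sample size or precision for DFS. The only fixed input is N = 20 (1.0 Trial Summary). The number of early stops in remission, and their relapse rate, are not given and enter below as assumptions.

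**Step 1: one subject under each text.** Take a subject in CR at day 77, stopped for toxicity during maintenance, who relapses some months later.

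- 5.6: disease status is followed and the relapse is dated.
- 7.1.4.5: sites are asked to try to collect it.
- Footnote †: 30-day toxicity assessment, then survival only.
- 7.1.4.5.1: survival status at least every 8 weeks.

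The first and third cannot both be followed.

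**Step 2: do other provisions supply the date?**

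- Footnote ‡ provides an unscheduled marrow on clinical suspicion during treatment and follow-up. It does not have relapse asked about or dated at each contact. Read literally, 7.1.4.3 also ends the Follow-up Period six months after treatment start.
- 7.1.4.1 asks for final-visit activities at discontinuation, while footnote § makes the early end-of-treatment marrow optional. Either way, an assessment at the stop cannot detect a later relapse.
- 7.1.1.5.3 has new anti-neoplastic therapy reviewed. This hints at a relapse but does not date it, and it misses an untreated one.

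These narrow the gap without closing it.

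**Step 3: size if the subject is counted as disease-free.** With no other censoring, the Kaplan-Meier estimate at 12 months is the proportion event-free.

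- Alive at 12 months with the relapse unrecorded: +1/20 = +5 percentage points.
- Missed relapse followed by death before 12 months: the death is an event, so the change at 12 months is 0. The event is only dated late.

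**Step 4: illustration (assumed pattern, not from the documents).** Of 20 subjects, 14 have events early, leaving S = 6/20 = 0.30. Three continue, and one of them relapses at month 9. Three stop in remission at month 5, and two of them relapse at month 8.

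- All relapses recorded: 0.30 × 4/6 × 3/4 = 0.15.
- Both missed, both alive at 12 months: 0.30 × 5/6 = 0.25.
- Both missed, one dies at month 11: 0.30 × 5/6 × 4/5 = 0.20.
- Both missed, both die at month 11: 0.30 × 5/6 × 3/5 = 0.15.
- The three stops censored at month 5: 0.30 × 2/3 = 0.20, which is 5 points too high.

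Now suppose none of the three stops relapses. The true value is 0.30 × 5/6 = 0.25, and censoring at month 5 still gives 0.20, which is 5 points too low. Under censoring, the direction depends on how the relapse risk of those who stop compares with that of subjects still followed.

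**Step 5: timing of the D365 marrow.** Section 8.1 starts the DFS clock at confirmed post-HCT relapse. Eligibility requires that relapse, so it precedes Day 1, and 12 months on the DFS clock falls before D365. Apart from the early edge of the ±14-day window, a relapse first found on the D365 marrow is dated after the 12-month mark.

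**The case against.** The best defence is that this is a wording mismatch in a summary table. Section 7.1 says the flow chart summarizes procedures that the text then describes in detail. Section 7.1.4.5.1 does not contain the word only, and it sits under 7.1.4.5, which asks for disease status. This is a single-center trial whose contacts are coordinated with routine BMT follow-up, so relapses would often be known. The analyses are descriptive, and the criteria for calling the drug promising use clinical benefit and CR, so no decision rests on DFS.

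Much of that stands. It limits the consequence and makes a missed relapse less likely. It does not remove the conflict between footnote † and 5.6, and knowing of a relapse in clinic is not the same as having a field in which to date it.

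The objection also disposes of several stronger readings that a reader might infer:

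- **One-year DFS is overstated.** The documents do not establish this. Section 8.1 gives no event or censoring rule, and Step 4 shows that the error can be zero or go either way.
- **The expected error is 5 to 15 points.** Fifteen points needs three subjects who stopped in remission, relapsed unrecorded and were alive at 12 months. The background section cites 13% one-year survival for AML relapsing 6 months after HCT. In 20 subjects that is 0.13 × 20 = 2.6 survivors in all. It is a different population, but it shows that three is not a neutral assumption.
- **The D365 marrow in maintenance completers drives a bias.** Step 5 shows that it mostly falls after the 12-month mark.
- **A comparison of DFS by GvHD is distorted.** Sections 8.1 and 8.2 plan none.

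**Conclusion.** The point holds in conditional form. Footnote † and 7.1.4.5.1 schedule survival status for subjects who stop without progression. Section 5.6 requires disease-status follow-up for them, and 7.1.4.5 asks for it. Followed as the flow chart is written, a relapse after an early stop can go undated, and one-year DFS and the relapse/progression regression can be biased.

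The size is 5 percentage points per unrecorded relapse, provided that N = 20, there is no other censoring, and the subject is alive at 12 months and counted as disease-free. It is 0 at 12 months if death follows within the year. It has no determined sign if such subjects are censored. How many subjects this would affect cannot be derived from the documents. The primary endpoints and the promising-drug criteria are untouched. It should be corrected because the endpoint is named and the data are cheap to collect prospectively.

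**What to change.** 1. Reconcile footnote † of 6.0 and section 7.1.4.5.1 with 5.6. For a subject who stops without progression, record relapse (yes/no, with date) and the start date of any new anti-leukemia therapy or DLI at the existing 8-weekly contacts, or the 12-weekly phone contacts, through one year. Move to survival-only follow-up after documented relapse or progression. Align the Follow-up Period in 7.1.4.3 in the same edit.
2. In 8.1, define the DFS event and censor subjects without an event at the last disease assessment. Say how the start of new therapy is handled, since 5.6 and 7.1.4.5 both end disease-status follow-up there.

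The cost is wording in a footnote and a few sections, and a few CRF fields at contacts already planned. Relapse can be taken from routine care records, so no marrow or visit is added and clinical management does not change.
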